4. STUDY DESIGN

4.1 Overall design

This is an open-label single arm study of olaparib + temozolomide for MGMT promoter hypermethylated CRC. Potentially eligible patients will be tested for MGMT promoter hypermethylation by methylation specific PCR after signing a pre-screening consent. If patients screen positive for MGMT promoter hypermethylation they will potentially be eligible for enrollment. The study will begin with a safety evaluation period as outlined in section 4.2 to assess tolerability of olaparib and TMZ in the study population. Throughout the study patients will continue with olaparib and temozolomide until objective disease progression (determined by RECIST v1.1) as long as in the investigator's opinion they are benefiting from treatment and they do not meet any other discontinuation criteria.

Once patients have been discontinued from study treatment, other treatment options will be at the discretion of the investigator.

For an overview of the study design see Figure 1, Section 1.3. For details on treatments given during the study, see Section 6.1 Treatments Administered.

For details on what is included in the efficacy and safety endpoints, see Section 3 Objectives and Endpoints. As detailed in the consent form, patients will be asked for authorization to send DNA samples to the National Institutes of Health (NIH) Database of Genotypes and Phenotypes (dbGaP) bank (or other NIH-funded database if indicated) where it can be used for future research projects as necessitated by funding agency regulations. All information will be de-identified prior to submission to the NIH dbGaP database (or other NIH-funded database if indicated).

4.2 Safety Evaluation Period

A safety evaluation period to assess for dose limiting toxicity (DLT) will be employed for at least the first 6 treated patients. Should excessive toxicity be observed at the starting dose, a dose de-escalation schema will be used for TMZ to 60 mg/m², while the olaparib will be maintained at the specified dose of 150 mg twice daily. Patients will be enrolled in cohorts of 3 during the safety evaluation period. For the first 3 patients treated on the study with olaparib 150 mg twice daily and TMZ 75 mg/m², if $\leq 1/3$ DLTs are observed, 3 additional patients will be enrolled at this dose and if $\leq 1/6$ DLTs are seen enrolment will proceed at this dose. If 2 or more DLTs are observed in either the first 3 or 6 patients treated at the starting doses, the TMZ dose will be decreased to 60 mg/m² with olaparib 150 mg twice daily. If 2 or more DLTs are seen in either the first 3 or 6 patients treated at TMZ 60 mg/m² with olaparib 150 mg twice daily then a further dose reduction to TMZ 50 mg/m² with olaparib 150 mg twice daily will be done. The doses of TMZ 50 mg/m² D1-7 with olaparib 150 mg twice daily have previously been tested as outlined in section 4.5. Therefore if the starting doses require reduction to TMZ 50 mg/m² D1-7 with olaparib 150 mg twice daily then safety will be assessed per the data safety monitoring plan as outlined in section 9.5.2.

The dose management tables throughout the protocol will be adjusted in an amendment as necessary if an alternate starting dose is identified. If a dose reduction is necessary, at least 9 patients (per early stopping rule) and up to 30 evaluable patients will be treated at the reduced dose as part of the efficacy analysis. Therefore in the case of a dose reduction the enrolment of 30 patients will be maintained at the same dose.

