4.4 Scientific rationale for study design

4.5 Justification for dose

The approved monotherapy dose of olaparib is 300 mg twice daily for the tablet formulation (Olaparib IB). However, when used in combination with additional systemic therapies the olaparib dose is often reduced (Olaparib IB). Temozolomide has numerous established dosage regimens pursuant to whether or not it is used in combination with additional systemic agents or radiotherapy (Refer to TMZ package insert). The combination of olaparib and TMZ has been studied in cell line and pre-clinical rodent models. Combination studies in rats suggested potential for olaparib to exacerbate the effects of TMZ, or topotecan, although combination for olaparib with these anticancer agents did not induce any additional target organ toxicities to those seen with single agent administration (Olaparib IB). Furthermore, the olaparib and TMZ combination is actively being investigated in humans in combination with TMZ in both small cell lung cancer and GBM. In GBM PARADIGM-2 is investigating various dose levels up to olaparib 150 mg twice daily (Days 1-5) and TMZ 75 mg/m² daily (continuous) with concomitant radiotherapy (Fulton, Short et al. 2017). Also in GBM the OPARATIC trial concluded continuous TMZ 75 mg/m² and olaparib 150 mg days 1-3 weekly was a safe dose for expansion (Halford, Cruickshank et al. 2017). This further supports the safety of continuous dosing. While in small cell lung cancer a 3+3 dose escalation identified olaparib 200 mg twice daily (Days 1-7) and TMZ 75 mg/m² (Days 1-7) as the recommended phase 2 dose of the combination (Farago, Drapkin et al. 2018). However, to achieve continuous PARP inhibition and PARP trapping, olaparib is being investigated with continuous dosing is being tested by Farago *et al.* At present doses of olaparib 150 mg twice daily (continuous) with TMZ 50-75 mg/m² daily (D1-7) are tolerable with no unanticipated toxicities although published data is unavailable at this time. Therefore, we will proceed with 21 day cycles of olaparib 150 mg twice daily (continuous – days 1-21) + TMZ 75 mg/m² (days 1-7) with a dose de-escalation schema if unacceptable toxicity is observed in the first 6 patients.

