8.4.3 Overdose

There is currently no specific treatment in the event of overdose with olaparib or TMZ and possible symptoms of overdose are not established.

Olaparib and TMZ must only be used in accordance with the dosing recommendations in this protocol. Any dose or frequency of dosing that exceeds the dosing regimen specified in this protocol should be reported as an overdose. The Maximum Tolerated Dose is Olaparib 150 mg mg twice daily (tablet) (Days 1-21) with TMZ 75 mg/m² (Days 1-7).

Adverse reactions associated with overdose should be treated symptomatically and should be managed appropriately.

- An overdose with associated AEs is recorded as the AE diagnosis/symptoms on the relevant AE modules in the CRF.

If an overdose on an AstraZeneca study drug occurs in the course of the study, then the Investigator or other site personnel inform appropriate AstraZeneca representatives immediately, or **no later than 24 hours** of when he or she becomes aware of it.

The designated AstraZeneca representative works with the Investigator to ensure that all relevant information is provided to AstraZeneca Patient Safety.

For overdoses associated with a SAE, the standard reporting timelines apply, see Section 8.3.2. For other overdoses, reporting must occur within 30 days.

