9.5.2 Safety Monitoring

The Yale Cancer Center Data and Safety Monitoring Committee (DSMC) will provide the primary oversight of data and safety monitoring. The Yale DSMC will review and monitor compliance, toxicity and deviations from this study. The committee is composed of clinical specialists with experience in oncology and who have no direct relationship with the study. Information that raises any questions about participant safety will be addressed with the Principal Investigator.

The DSMC will review this protocol at a minimum of once every six months. Information to be provided to the committee includes: a study narrative by the PI, a summary DSMC report produced by OnCore (which includes participant accrual, response, trial status history, SAEs, Adverse Events, Deviations and survival); audit results, and monitoring reports as applicable. Other information (e.g. scans, laboratory values) will be provided upon request.

The Yale DSMC will perform an interim safety analysis after 15 patients have received at least 1 cycle (28 days) of treatment to determine whether there are any safety issues and to assess whether it is safe to continue enrollment. Enrollment will be suspended until approval is granted from the DSMC to proceed completion of enrollment.

If a new unexpected toxicity is identified from the above safety review, or if the periodic review of all the adverse events and laboratory data raises safety concerns, it may result in revision of the consent form, amendment of the protocol and/or suspension of the protocol.

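### TMZ 50 mg/m² is reached only after two levels have failed their DLT count, yet it is the one level with no DLT count, for a stated reason that does not single it out

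*Combined protocol and SAP*

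**What the plan says.** Section 4.2 enrols in cohorts of three and sets the same trigger at the first two TMZ levels, with olaparib held at 150 mg twice daily throughout. The trial leaves 75 mg/m² "If 2 or more DLTs are observed in either the first 3 or 6 patients treated at the starting doses". It leaves 60 mg/m² on the same terms: "If 2 or more DLTs are seen in either the first 3 or 6 patients treated at TMZ 60 mg/m²".

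For 50 mg/m² the section gives a reason and a substitute. The reason is that these doses "have previously been tested as outlined in section 4.5". The substitute is that, if TMZ has to come down to 50 mg/m² "with olaparib 150 mg twice daily then safety will be assessed per the data safety monitoring plan as outlined in section 9.5.2".

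Three other places bear on this:

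- Section 4.5 states: "At present doses of olaparib 150 mg twice daily (continuous) with TMZ 50-75 mg/m² daily (D1-7) are tolerable with no unanticipated toxicities". It adds that no published data are available, and then adopts 75 mg/m² as the starting dose.
- Section 9.5.2 has the DSMC review the study at least every six months. The DSMC also "will perform an interim safety analysis after 15 patients have received at least 1 cycle", with the cycle given as 28 days. Enrolment is suspended at that point until the DSMC approves continuing.
- Section 8.4.3 states: "The Maximum Tolerated Dose is Olaparib 150 mg mg twice daily (tablet) (Days 1-21) with TMZ 75 mg/m² (Days 1-7".

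Section 4.3 limits DLT determination to the first 21-day cycle of patients in the safety evaluation period. Section 4.2 also plans at least 9 and up to 30 evaluable patients at a reduced dose.

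**The concern.** The third level is reached only if this trial has seen 2 or more DLTs at each of the first two. That is the branch with the strongest toxicity signal, and it is where the early count is dropped.

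The reason for dropping it is not specific to 50 mg/m². The statement in section 4.5 names 75 mg/m² as the top of its range and takes in 60 mg/m² by falling inside it. If that statement were enough to waive the count at 50, it would have been enough at 75 and 60, where the plan did not rely on it. By the time it is used, the trial's own data would have weakened it.

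At stake is whether a cluster of first-cycle toxicity at the dose that goes on to carry the efficacy test would prompt a defined response early, or only when a general review falls due.

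**Working it through.** The documents give no operating characteristic for the DLT rule and no expected DLT rate, so there is no stated figure to reproduce. The finding rests on the text; the probabilities show scale only.

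**1. How safety is judged at each level**

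| TMZ level | Early cohort | Trigger | Source |
|---|---|---|---|
| 75 mg/m² | 3, then 6 | 2 or more DLTs | 4.2 |
| 60 mg/m² | 3 or 6 | 2 or more DLTs | 4.2 |
| 50 mg/m² | none stated | none stated; refers to 9.5.2 | 4.2, 9.5.2 |

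The opening of section 4.2 promises a DLT evaluation for at least the first six treated patients. That does not secure a cohort at 50 mg/m²: the earlier levels use at least 3 + 3 = 6 patients.

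**2. Chance that a level meets the trigger.** With true DLT rate p, stopping at 3 or 6 patients gives the same probability as 2 or more of 6:

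P(fail) = 1 − (1−p)^6 − 6p(1−p)^5

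- p = .20: 1 − .262 − .393 = .345
- p = .30: 1 − .118 − .303 = .580
- p = .40: 1 − .047 − .187 = .767

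**3. Chance of reaching 50 mg/m².** If p is the same at 75 and 60 (an assumption), this is P(fail) squared:

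- p = .20: .345² = .12
- p = .30: .580² = .34
- p = .40: .767² = .59

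With an assumed falling gradient of 40%, 33% and 25% at 75, 60 and 50, it is .767 × .642 = .49. A count of 2 or more of 6 at 50 would then occur with probability .466.

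**4. What the hold at 15 patients sees.** Each failed level uses 3 or 6 patients, so 6 to 12 in total before any replacement.

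- If the 15 are all treated patients: 15 − 12 = 3 to 15 − 6 = 9 have been treated at 50 mg/m².
- If the 15 are patients at 50 mg/m²: 15 are treated there before the hold.

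The range 3 to 9 is approximate. Section 4.3 allows patients not evaluable for DLT to be replaced, which can raise the number treated earlier and lower the number at 50.

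**5. Cycle length.** Section 9.5.2 counts a cycle as 28 days. The treatment cycle (section 1.2) and the DLT window (section 4.3) are 21 days.

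**6. The maximum tolerated dose.** Section 8.4.3 presents olaparib 150 mg twice daily with TMZ 75 mg/m² as the established maximum tolerated dose, while section 4.2 is still testing that combination and provides for its failure.

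**The case against.** The plan discloses this choice and names the substitute. Patients at 50 mg/m² are not unmonitored: enrolment stops at 15 patients whatever the toxicity, the DSMC can act at its six-monthly reviews, and a safety concern can suspend the protocol. The look at 9 evaluable patients can end the trial for futility. Individual interruption and dose-reduction rules (sections 6.6 and 8.4.5) continue and include steps for a 50 mg/m² start. On the reading that counts all treated patients, the hold comes when few have received 50 mg/m². All of this stands and limits the point.

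It also rules out several stronger readings that a reader might infer:

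- **That nothing could stop some 30 patients being treated at 50 mg/m².** The documents do not support this, because the hold and the futility look come first. What is absent is an early rule tied to DLTs at that level.
- **That two failed levels disprove the tolerability statement.** The trigger is strict: a level with a true DLT rate of 20% meets it with probability .345. Failure weakens the statement as grounds for a waiver; it does not refute it for a lower dose.
- **That the expected DLTs among 30 patients (6, 9 or 12 at rates of 20%, 30% or 40%) measure the harm.** That is total burden, not the excess due to the missing count.
- **That the 15 should simply be counted at the dose carried forward.** This could move the hold later than it now falls.

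The objection does not supply what is missing. The 9-patient look tests response, not safety. Individual dose changes are not a decision about the level. Section 9.5.2 has no threshold and does not say which dose its 15 patients received. Nor does a lower TMZ dose settle the matter: olaparib is unchanged, and section 2.3.1 reports more marrow toxicity with olaparib-chemotherapy combinations than expected from the agents alone.

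**Conclusion.** The concern holds in a limited form. If 50 mg/m² is reached, the plan has no early, pre-specified safety check at that level, although it has one at both levels above. The stated reason does not distinguish 50 mg/m² from the levels that would have failed.

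The gap is conditional on two failures. Under an assumed common DLT rate of 20%, 30% or 40% at 75 and 60 mg/m², that has probability .12, .34 or .59. Before the hold, about 3 to 9 patients would be treated at 50 mg/m² on one reading of section 9.5.2 and 15 on the other. The textual finding does not depend on the assumed rates.

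This should be fixed, because it concerns patient safety and is cheap to close. Given the remaining safeguards and the conditional nature of the gap, it does not by itself undermine the design.

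**What to change.** - Reconcile sections 4.2, 4.3, 4.5 and 9.5.2 on how first-cycle safety is judged at the third level. Either make it consistent with the first two levels, or give a rationale that would still hold after both have failed.
- State in section 9.5.2 which patients, and which dose level, the 15 counts, without making the enrolment hold later than it is now.
- Correct the cycle length in section 9.5.2 so that it agrees with the 21-day cycle used elsewhere.
- Reconcile the maximum tolerated dose sentence in section 8.4.3 with section 4.2, which is still evaluating that combination.

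The rule itself, and what follows a failed third level, are for the sponsor and the DSMC to decide. The cost is protocol wording and possibly a short accrual pause, only if the third level is reached. No extra patients are needed, since those first treated at that level would be enrolled anyway.

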4.3 Dose Limiting Toxicity Definition

Dose limiting toxicities will be determined on events that occur during the first 21-day cycle for patients in the safety evaluation period.

Any adverse event of Grade 3 or higher that is at least “possibly related” to olaparib or TMZ will be considered a DLT, unless there is a clear alternative explanation as to the cause of the AE (e.g., disease related), as well as the following conditions:

- Delays of > 7 consecutive days that occurs as a result of TMZ or olaparib.

- Grade 3 mucositis, nausea, vomiting, or diarrhea, AST/ALT elevation will only be considered a DLT if it lasts more than 72 hours despite optimal supportive care.
- Grade 4 mucositis, nausea, vomiting, and diarrhea will be considered DLTs if they reach grade 4 severity despite optimal supportive care, irrespective of duration.
- Any grade 4 hematologic toxicity with the following exceptions:
 - Grade 4 neutropenia will only be considered a DLT if it lasts \geq 7 days
- Any febrile neutropenia will be considered a DLT.
- Any adverse event that meets the definition of Hy's Law.
- Hypersensitivity/Infusion reactions will not be considered a DLT (hypersensitivity reactions are generally not related to the dose level of the drug since they can occur even

Subjects who do not complete both 75% of the TMZ and 75% of the olaparib doses in the 21-day DLT evaluation period, due to reasons other than occurrence of DLT(s) will be considered non-evaluable for DLT, and may be replaced to ensure the accrual of the minimum number of subjects to adequately assess tolerability as outlined in the safety evaluation period.

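### Section 4.3 contradicts itself on neutropenia: read literally, a short grade 3 is a DLT and a short grade 4 is not, and the status of short grade 3 anaemia and thrombocytopenia depends on the reading

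*Combined protocol and SAP*

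**What the plan says.** Section 4.3 counts events in the first 21-day cycle. Its lead sentence begins "Any adverse event of Grade 3 or higher that is at least" possibly related to olaparib or TMZ, and makes each such event a DLT unless another cause is clear. The bullets are attached as further conditions, but they do different jobs:

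- Some add events: "Delays of > 7 consecutive days that occurs as a result of TMZ or olaparib", Hy's Law cases, and "Any febrile neutropenia will be considered a DLT".
- Some restrict the lead sentence: grade 3 mucositis, nausea, vomiting, diarrhoea or AST/ALT elevation "will only be considered a DLT if it lasts more than 72 hours despite optimal supportive care".
- One excludes: hypersensitivity reactions are not DLTs.
- The haematologic bullet reads "Any grade 4 hematologic toxicity with the following exceptions". The one exception listed is "Grade 4 neutropenia will only be considered a DLT if it lasts" at least 7 days. Grade 3 haematologic toxicity is not mentioned.

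The evaluability rule in the same section covers "Subjects who do not complete both 75% of the TMZ and 75% of the olaparib doses in the 21-day DLT evaluation period", where the shortfall is "due to reasons other than occurrence of DLT(s) will be considered non-evaluable for DLT, and may be replaced".

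Under section 4.2, two or more DLTs in the first 3 or 6 patients lower TMZ to 60 mg/m², with olaparib unchanged. At least 9 and up to 30 evaluable patients are then treated at the reduced dose for the efficacy analysis.

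**The concern.** A DLT definition should rank events by severity, and this one reverses the order for neutropenia. The reversal also defeats the exception: a grade 4 neutropenia that recovers passes through grade 3, and Appendix B6 asks for every grade change to be reported. If grade 3 of any duration counts, the allowance for a short grade 4 has almost no effect.

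For grade 3 anaemia and thrombocytopenia the lead sentence says yes. The haematologic bullet implies no, because a separate grade 4 rule would be nearly redundant if grade 3 already counted.

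Marrow toxicity is a foreseeable event in this run-in. Section 2.3.1 reports that olaparib combined with chemotherapy increases it beyond what the single agents would produce. Section 4.5 says published data for the continuous schedule are not yet available. The same observed events could therefore lead to two different trial doses, with the choice made in an open-label study after the events are known.

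**Working it through.** **Step 1. The two readings side by side.** All events are at least possibly related, with no clear alternative cause. Reading A applies the text literally. Reading B lets the haematologic bullet set the threshold.

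| Event in cycle 1 | A | B |
|---|---|---|
| Afebrile grade 3 neutropenia, hold of 7 days or less | DLT | not a DLT |
| Afebrile grade 4 neutropenia under 7 days, hold of 7 days or less | not a DLT (though its grade 3 phase would be) | not a DLT |
| Grade 3 anaemia or thrombocytopenia, hold of 7 days or less | DLT | not a DLT |
| Grade 4 neutropenia of 7 days or more | DLT | DLT |
| Other grade 4 haematologic toxicity | DLT | DLT |
| Febrile neutropenia | DLT | DLT |
| Any cytopenia with a treatment-caused hold of more than 7 consecutive days | DLT | DLT |

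The last row rests on the protocol's own usage. Section 1.1 speaks of dosing being delayed for adverse events under the toxicity guidelines, and section 8.4.5.1 pairs interruption with delay as one concept. The dispute is therefore limited to short holds.

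**Step 2. Effect on the section 4.2 decision.** Two DLTs among the first 3 are also two among 6, so the final rule is: reduce if 2 or more of 6. Let u be the patients with an undisputed DLT and d those with only a disputed cytopenia. Assume the disputed patients remain evaluable.

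- Reading A reduces if u + d ≥ 2; reading B reduces if u ≥ 2.
- They disagree when u = 0 and d ≥ 2, or when u = 1 and d ≥ 1.
- With u + d ≤ 6 there are 7 × 8 / 2 = 28 possible pairs. The readings disagree in 10: (0,2) to (0,6) and (1,1) to (1,5). These are counts of patterns, not probabilities.

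**Step 3. Interaction with the 75% rule.** Table 12 requires dosing to stop at grade 3-4 neutropenia, leukopenia or thrombocytopenia until grade 1 or better.

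- Olaparib: 2 × 21 = 42 doses. Missing 10 leaves 32/42 = 76.2% (evaluable). Missing 11 leaves 31/42 = 73.8% (not evaluable).
- 11 missed doses is 5.5 days and 14 is 7.0 days. A hold of 5.5 to 7.0 days fails the 75% rule without reaching the delay bullet.
- Example: grade 3 neutropenia on the day 15 count, olaparib held through day 21 and restarted at cycle 2 day 1. Then 14 doses are missed, 28/42 = 66.7%.
- TMZ has 7 doses: 6/7 = 85.7% passes and 5/7 = 71.4% fails.

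Under reading A the example patient is a DLT. Under reading B the shortfall has a cause other than a DLT, so the patient may be replaced and leaves the safety count.

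**Step 4. The efficacy design.** The two-stage rule (stop at 0 of 9, reject at 4 or more of 30), computed exactly, gives alpha 0.0489, power 0.902, early stopping 0.630 and expected size 16.8. The plan states .049, 90%, 63% and 17. None of these depends on the DLT definition.

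**The case against.** **Intent is clear enough.** Several bullets override the lead sentence, the grade 4 bullet makes little sense otherwise, and a single-institution team would probably apply it that way. The intent argument stands. It does not remove the contradiction, because where the authors wanted to relax a grade 3 event (GI, AST/ALT) they said so, and for cytopenias they did not.

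**Section 8.3.7 may resolve it.** It reports laboratory deteriorations as AEs only if they are serious or the reason for discontinuation, so laboratory-only cytopenias might never reach the lead sentence. Section 9.4.2, which lists grade 3-4 laboratory abnormalities beside AEs, fits that. This is supporting evidence, not an answer. AST and ALT are also protocol-mandated values (Table 10), yet section 4.3 gives them a grade 3 restriction. Section 8.4.5.1 speaks of neutropenia as an adverse event, and Appendix B1 offers an abnormal laboratory finding as an example of one. Appendix B5 lists anaemia needing transfusion among important medical events, and Table 11 names transfusion for grade 3 anaemia, so such a case can pass the 8.3.7 filter.

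**The text may be incomplete.** The hypersensitivity bullet breaks off, and the haematologic bullet announces exceptions in the plural but lists one. This may come from the PDF reading. A further exception under a grade 4 bullet would narrow grade 4 and would not, by itself, limit the lead sentence.

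**Stronger readings the documents do not support.** A reader might infer that toxicity holds escape the delay bullet; sections 1.1 and 8.4.5.1 indicate otherwise. A reader might also take 10 of 28 as a risk. It is not: the patterns are not equally likely, and no document gives a DLT or cytopenia rate. With assumed rates of 5% to 20% for undisputed DLTs and 2% to 20% for disputed cytopenias, the probability that the two readings give different doses runs from 0.028 to 0.466, which shows only that it is undetermined.

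**Conclusion.** The definition is wrong as written for neutropenia and ambiguous for uncomplicated grade 3 anaemia and thrombocytopenia, in each case only where dosing is held for 7 days or less. The consequence is a possible difference in the TMZ dose given to the efficacy cohort, and a route by which a patient with treatment-related marrow toxicity can be replaced. How often either would happen cannot be said from the documents.

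Severity is minor to moderate. The wording governs cycle 1 of a small run-in, and the lower doses are pre-specified. The literal reading errs toward the lower dose. Section 9.5.2 suspends enrolment for a DSMC safety review after 15 patients, although that review follows the dose decision and does not define a DLT.

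A reader might infer that the primary analysis is compromised. It is not: the definition can affect the dose at which response is tested, but not the test or its error rates.

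The conclusion assumes that the section 4.3 text is substantially complete and that interruptions count as delays, as the protocol's usage indicates.

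**What to change.** Revise section 4.3 before the run-in:

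1. Limit the lead sentence to non-haematologic adverse events.
2. List haematologic DLTs separately: grade 4 neutropenia lasting at least 7 days; any other grade 4 haematologic toxicity; febrile neutropenia; and any grade 3 cytopenia the investigators choose to include, with its conditions. Which of these to include is a clinical decision.
3. State that these are counted from laboratory values, whether or not section 8.3.7 would have them reported as AEs.
4. State that a patient who falls below 75% of either drug's doses because of a treatment-related cytopenia is not replaced as non-evaluable.

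The GI, AST/ALT and hypersensitivity bullets need no change of substance, and no separate statement on interruptions and delays is needed. The cost is the wording of one section, with no extra patients, visits or procedures.
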